5.9 Pregnancy Related Definitions

The date of conception will be estimated for each reported pregnancy by the Principal investigator. This estimated date of conception will be used to determine whether the pregnancy was pre-, on- or post-treatment. In addition, the estimated date of conception will be reviewed alongside the compliance data recorded on the subject diary and the pregnancy narrative completed by the PI to determine whether the pregnancy occurred in a compliant (Product Failure) or non-compliant (User-Failure) subject with compliance suggesting method failure and non-compliance suggesting user failure. The definitions of pre-, on- and post-treatment pregnancies and for method and user failure pregnancies are provided below.

5.9.1 Pre-Treatment Pregnancies

Pre-treatment pregnancies are pregnancies with an estimated date of conception before the date of the first dose of study medication.

5.9.2 On-Treatment Pregnancies

On-treatment pregnancies are pregnancies with an estimated date of conception during the On-Treatment Period for contraceptive efficacy (see Section 5.3 for the definition of the On-Treatment Period). In cases where the date of conception cannot be established unequivocally (e.g. subjects is lost to follow up), this pregnancy will be considered as on-treatment pregnancy.

For on-treatment pregnancies, the cycle and day within the cycle of conception will be assigned based on the diary data collected and the estimated conception date. If the on-treatment pregnancy has an estimated date of conception in the 7-days after the last dose of study medication, then the cycle of conception will be the cycle in which the last dose of study medication was taken and the day of conception will be not applicable.

5.9.3 Post-Treatment Pregnancies

Post-treatment pregnancies are pregnancies with an estimated date of conception after the end of the On-Treatment Period for contraceptive efficacy.

5.9.4 Method and User Failure Pregnancies

User failure pregnancies are pregnancies where the subject did not take the study medication correctly as per Section 9.4.4 of the Protocol during the cycle in which the estimated date of conception occurred or used drugs that have the potential to trigger interactions with COC (Section 9.4.6 of the Protocol). Pregnancies not identified as due to user failure will be considered to be method failure pregnancies. The pregnancy narratives from the Principal Investigator are used to determine whether a pregnancy is a user or method failure pregnancy.

Each on-treatment pregnancy will be reviewed in conjunction with the data collected and classified as either a method failure or a user failure pregnancy prior to database lock.

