9.4.4.2 Dosing Instructions

Each time investigational product is dispensed to the subject, site personnel will instruct the subject as follows:

- Take one pink tablet every day for 24 consecutive days (Day 1 through Day 24), followed by one white placebo tablet every day for 4 consecutive days (Day 25 through Day 28).
- When the pack of tablets is empty, start the next pack on the next day after the last white tablet of the previous pack has been taken. When starting a new pack of tablets, take the first pink tablet of the pack. There should be no interruption between two blister packs.
- Take the investigational product at approximately the same time each day throughout the study. The time of day should be determined by the subject.
- Return all blister packs to site personnel at the following visit.

9.4.4.3 Instructions in case of missed tablet(s) or in conditions potentially reducing the contraceptive efficacy

If the subject has vomiting or diarrhea within 4 hours of tablet intake, she should take another tablet from the extra pack (spare blister) as a replacement.

If the subject inadvertently misses one or more of the tablets, the following instructions must be followed⁶:

- If one active pink tablet is late (< 24 hours since a tablet should have been taken) or if one active pink tablet has been missed (24 to < 48 hours since a tablet should have been taken):
 - Take the late or missed active pink tablet as soon as possible.
 - Continue taking the remaining active pink tablets at the usual time (even if it means taking two active pink tablets on the same day).
 - Use of condom is not required.
- If two or more consecutive active pink tablets have been missed (\geq 48 hours since a tablet should have been taken):
 - If between Day 1 & Day 17:
 - Take the most recent missed active pink tablet as soon as possible (any other missed tablets should be discarded).
 - Continue taking the remaining active pink tablets at the usual time (even if it means taking two tablets on the same day).
 - Use condom or avoid sexual intercourse until 7 days of uninterrupted active pink tablet intake.
 - Consider emergency contraception as per current practice if the woman had unprotected intercourse during the missed pill interval.
 - If between Day 18 & Day 24:
 - Omit the hormone-free interval by finishing the active pink tablets in the current pack and starting a new pack the next day.

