12.4 Efficacy Analyses

The efficacy analysis will be based on the Pearl Index. The Pearl Index, defined as the number of pregnancies per 100 women-years of treatment, will be calculated as

 $Pearl Index = \frac{1300 \times \text{number of on} - \text{treatment pregnancies}}{\text{number of women} - 28 \text{ day equivalent cycles of treatment}}$

Only at risk cycles, i.e. cycles in which no other methods of birth control (including condoms) are used and during which the subjects confirmed that sexual intercourse has occurred, will be included in the denominator of the Pearl Index calculation. The subject diary data will be used to determine whether additional birth control methods were used and whether the subject has had intercourse.

Note that if conception occurs in a cycle, then that cycle will be included in the denominator even if other methods of birth control were used during that cycle or the subject did not confirm that they had had sexual intercourse. Cycles after the cycle of conception will be excluded from the denominator. All on-treatment pregnancies will be included in the numerator for the Pearl Index.

On-treatment pregnancy is defined as pregnancy with an estimated date of conception within the on-treatment period, i.e. Day 1 to 7 days after the intake of investigational product (whether active or inactive tablet). In cases where the date of conception cannot be established unequivocally (e.g. subjects is lost to follow-up), this pregnancy will be considered an on-treatment pregnancy. For calculation purposes a cycle will be defined as 28 days.

The method failure Pearl Index is calculated using the same method as the Pearl Index, but includes only those pregnancies that were classified as method failure and not pregnancies due to user failure, i.e. incorrect intake of the contraceptive product. Compliance data will be used to determine if the pregnancy was due to user failure.

Each on-treatment pregnancy will be reviewed and classified as either a method failure or a user failure pregnancy prior to database lock. Pregnancies will only be designated as user

failures if there is documentation that the subject did not use the test article correctly during the treatment cycle the conception occurred, including the instructions to be followed in case of missed pill(s).

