- 4. The subject does not receive unauthorized concomitant medication (see section 9.4.6.1 of the protocol) for at least one day during the cycle
- 5. The subject does not miss 4 or more days of active pills during the cycle
- 6. The subject does not miss 2 or more consecutive days of active pills during the cycle
- 7. The length of the previous cycle is not longer than 28 days
- 8. The subject had no adverse events of vomiting and/or diarrhea during the cycle

In the second of these definitions, cycles qualify if they meet all of the criteria 1 and 3 to 8 listed above (i.e. occurrence of sexual intercourse is not taken into account),

The following rules will be applied to all types of exposure:

- If conception occurs in a cycle, then that cycle will be included in the denominator, regardless of whether or not other methods of birth control were used during that cycle, or whether or not sexual intercourse was confirmed.
 - If the conception is confirmed to be during a specific cycle in the narrative and this cycle is not in the diary data, then the cycle will be included in the denominator, regardless of whether or not other methods of birth control were used during that cycle, or whether or not sexual intercourse was confirmed
 - The only exception is for user failure pregnancies, which will be excluded from the exposure definitions based on the compliance rules 3 to 8 above, since they do not meet criterion 3
- Cycles after the cycle of conception will be excluded from the denominator
- Missing data from the diary will be handled according to section 5.15.1.

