9.5.2.2 Method Failure Pearl Index

The method failure Pearl Index is calculated using the same method as the Pearl Index (see Section 9.5.1 for details), but includes only those pregnancies that were classified as method failure (see Section 5.9.4 for details). Pregnancies due to user failure will be excluded from the numerator.

The method failure Pearl Index and corresponding 95% CIs will be presented for subjects aged 16 to 35 years at Screening in the ITT Population and for all subjects in the ITT Population including only at-risk cycles in the denominator. The number of on-treatment pregnancies and at-risk cycles will be presented.

This will be derived in 4 ways:

- Including all at-risk cycles in the denominator where at-risk cycles will be defined as cycles in which no other methods of birth control (including condoms and emergency contraception) are used by the subject as confirmed in the subject diary and the subject confirmed that sexual intercourse occurred during the cycle in the subject diary.
- Including all at-risk cycles in the denominator employing a modified at-risk definition. With this
 definition, at-risk cycles will be defined as cycles in which no other methods of birth control
 (including condoms and emergency contraception) are used by the subject while cycles with and
 without confirmed intercourse are being included in the denominator.
- Including only at-risk cycles in the denominator where at-risk cycles will be defined as cycles in which no other methods of birth control (including condoms and emergency contraception) are used by the subject as confirmed in the subject diary and the subject confirmed that sexual intercourse occurred during the cycle in the subject diary where the subject was compliant with the dosing rules 3 to 8 in Section 5.1.1.
- Including only modified at-risk cycles in the denominator where at-risk cycles will be defined as cycles in which no other methods of birth control (including condoms and emergency contraception) are used by the subject as confirmed in the subject diary where the subject was compliant with the dosing rules 3 to 8 in Section 5.1.1 while cycles with and without confirmed intercourse are being included in the denominator.

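### The two compliance-based method-failure Pearl Indices screen pregnancies and cycles by different definitions of incorrect use, so neither is a rate in one defined set of compliant cycles

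*SAP*

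**What the plan says.** **Numerator.** SAP 5.9.4 calls a pregnancy a user failure if the woman "did not take the study medication correctly as per Section 9.4.4 of the Protocol during the cycle in which the estimated date of conception occurred"; use of interacting drugs is the other ground. Everything else is a method failure. The source is case review: "The pregnancy narratives from the Principal Investigator are used to determine whether a pregnancy is a user or method failure pregnancy". Protocol 12.4 treats the missed-pill instructions as part of correct use and allows the user-failure label only where incorrect use is documented.

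**What Protocol 9.4.4 asks.** One active tablet daily on Days 1 to 24, and a single late or missed one taken as soon as possible. After two or more consecutive misses there are separate instructions by cycle day. For gastrointestinal events, 9.4.4.3 provides a replacement tablet in a sentence that opens "If the subject has vomiting or diarrhea within 4 hours of tablet intake, she should take another tablet from the extra pack (spare blister) as".

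**Denominator.** The third and fourth derivations in SAP 9.5.2.2 keep cycles "where the subject was compliant with the dosing rules 3 to 8 in Section 5.1.1". Criteria 4 to 8 remove a cycle for unauthorized medication, missed active tablets, a previous cycle over 28 days, or a gastrointestinal event. There are two missed-tablet limits. One reads "The subject does not miss 4 or more days of active pills during the cycle"; the other removes a cycle at two or more consecutive missed active days. Criterion 8 reads "The subject had no adverse events of vomiting and/or diarrhea during the cycle". Criterion 3 removes the conception cycle of a user-failure pregnancy. The rules after the criteria keep every other conception cycle in the denominator.

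**The concern.** A Pearl Index is interpretable when a pregnancy can be counted if and only if the cycle it arose in is counted. Here a cycle's compliance status depends partly on its outcome.

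Take two women who each leave out three separate active tablets and never make them up. The one who conceives can be classed as a user failure, and both her pregnancy and her cycle are removed. The one who does not conceive keeps her cycle as compliant.

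Now take two women with a vomiting event who each take the replacement tablet. The one who conceives is a method failure and her cycle is kept. The other woman's cycle is dropped.

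The first mismatch lowers the index and the second raises it. These two derivations are the ones meant to describe failure under compliant use, and the method-failure Pearl Index is a stated secondary objective.

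**Working it through.** **The plan's own figures.** The documents give no design figure for the method-failure index, so the only ones to reproduce are those for the overall index.

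- Upper limit from SAP 9.5.1: 1300 × ½χ²(0.975; 2(x+1)) / cycles. Power is the probability that this limit exceeds the Pearl Index by at most 1, with x Poisson with mean cycles/1300 (true index 1.0).
- At 12,336 cycles up to 13 pregnancies meet the target and power is 0.8988. At 12,337 cycles up to 14 do and power is 0.9404. Power moves in steps (it is 0.9139 at 12,000), but it stays above 0.90 from 12,337 onward (checked to 20,000). The stated 12,337 is reproduced.
- Planned cycles, ages 16 to 35: 990 × 13 + 810 × 4 = 16,110 in all. At 80% at risk, 0.8 × 16,110 = 12,888.

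**The two rules side by side**

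| Event in the cycle | Pregnancy in that cycle | Cycle without conception |
|---|---|---|
| 1–3 isolated active tablets missed, taken late as instructed | Method failure, counted | Kept: consistent |
| 1–3 isolated active tablets missed, never made up | Can be user failure, pregnancy and cycle removed | Kept: mismatch, lowers the index |
| Vomiting or diarrhea event, replacement tablet taken | Method failure, pregnancy and cycle kept | Removed: mismatch, raises the index |
| Two or more consecutive misses, instructions followed | Method failure if following them is correct use | Removed: mismatch, raises the index |

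The last row bites only where the woman abstained, or where the misses fell on Days 18 to 24 and no condom was needed. Recorded condom use already removes a non-conception cycle under criterion 1.

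**Size.** Let D be the planned compliant denominator and x the method failures. Let s be the share of D with the lapse in row two. Let u be the number of correctly used cycles removed under rows three and four, as a fraction of D. If every pregnancy in a row-two cycle is labelled user failure, the set of correctly used cycles is D(1 − s + u), and

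planned index / matched index = [1300x/D] / [1300x/(D(1 − s + u))] = 1 − s + u.

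Neither s nor u is in the documents; the values below are assumptions.

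- u = 0: ratio 0.95 at s = 5%, 0.90 at 10%, 0.70 at 30%.
- s = 0: ratio 1.10 at u = 10%.
- s = u: ratio 1.00.

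Illustration for the third derivation, with an assumed 5 method failures and D = 12,888 (an upper bound, since criteria 3 to 8 remove cycles): planned 1300 × 5/12,888 = 0.50, upper limit 1.18. The matched figure is 1300 × 5/(12,888 × 0.9) = 0.56 at s = 10%, u = 0, and 1300 × 5/(12,888 × 1.1) = 0.46 at s = 0, u = 10%.

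**Effect of reclassifying one pregnancy.** In the third derivation it is at least 1300/12,888 = 0.10. In the fourth, which also admits cycles without confirmed intercourse, it is at least 1300/16,110 = 0.08.

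**Comparison with the other derivations.** The third has the first's numerator and a subset of its denominator; the fourth stands in the same relation to the second. So third ≥ first and fourth ≥ second, for the estimate and both confidence limits.

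**The case against.** The strongest reply has four parts.

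- **The filter is not arbitrary.** Protocol 9.4.4.3 itself separates one missed tablet from two or more consecutive ones, and the consecutive-miss criterion follows that boundary. This stands. A single tablet taken late is correct use and its cycle is rightly kept. What remains is the tablet never made up, for which no tolerance is written into SAP 5.9.4.
- **Review before lock will settle it.** SAP 8.3 reviews at-risk status only where the rules leave it unclear. The missed-tablet limits give a clear answer, and only pregnancies have narratives. Nothing tells those classifying pregnancies to apply the same limits.
- **The reach is small.** This stands. Two of four secondary derivations are affected. The index that Protocol 12.4 defines is the first derivation, and SAP 9.0 plans no formal statistical analyses.
- **Replacing the planned figures could do harm.** This also stands. Applying criteria 4 to 8 to pregnancies drops some true method failures. Because SAP 5.15.1 reads blank intake as not taken, it would also drop pregnancies with missing diaries. Hence the proposal is an additional figure with its own missing-diary rule.

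A reader might infer that the compliance-based indices flatter the product. The documents do not support that: the mismatches oppose each other, and neither index can be more favourable than its unrestricted counterpart.

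**Conclusion.** The mismatch is in the current text and no other passage reconciles it. The third and fourth method-failure Pearl Indices are therefore not failure rates in any one defined set of compliant cycles.

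The net direction and size cannot be determined from the documents. The factor 1 − s describes the first mismatch alone and rests on two assumptions: the value of s, and that every pregnancy after such a lapse is labelled user failure. A reader might take 10% or 30% as an estimate of bias; these are only the results of assumed shares.

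A reader might also extend the point to the main efficacy result. That would be wrong: the primary Pearl Index, the sample size and the first two method-failure derivations do not use criteria 3 to 8. The change is worth making before database lock, but it is a secondary matter.

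**What to change.** Keep the four planned derivations. Beside the third and fourth, add a matched figure labelled as pregnancies per diary-compliant cycle, specified in SAP 5.1.1 and 9.5.2.2 as follows.

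1. Criteria 4 to 8 apply identically to cycles with and without a conception. A pregnancy and its cycle count only if the cycle passes, except as in item 4.
2. Criterion 3 becomes: no cycle after a conception.
3. Conception cycles stay exempt from criteria 1 and 2, as now planned.
4. Where diary data for the conception cycle are blank or absent, the pregnancy and its cycle stay in unless incorrect use is documented, in line with Protocol 12.4.
5. The narrative classification continues to govern the first two derivations.

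The cost is SAP wording and a small extra analysis that reuses flags already derived. Some pregnancies classed as user failures from the narrative will count and some classed as method failures will drop out, so the matched figure may move either way.

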In addition, the subject diary data will be used to identify when a pill has been missed. The number of missed pills will be derived for each cycle. In this situation, a pill is assumed to be missed if there is a day in the diary without an entry for the number of tablets or with 0 active and 0 inactive pills reported as taken. Any gaps between Day 28 of a cycle and Day 1 of the next cycle will be included as missed pills. For example, if the reported start date for Cycle 1 is 1 February and the reported start date for Cycle 2 is 3 March, then the derived end date of Cycle 1 will be 2 March and 1-2 March will be included as 2 missed pills. If there are overlapping cycles in terms of dates, then the days will be included under the latest cycle and missed pills will be reported accordingly. For example, if the subject takes pills up to Day 24 in Cycle 1, then starts Cycle 2 on the same date as Day 25 of Cycle 1, so Days 25 to Day 28 of Cycle 1 will not be included in Cycle1 and these will not be counted as missed pills for Cycle 1.

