5.15 Methods for Handling Missing Data

5.15.1 Missing Data Related to the Pearl Index and Pill Intake

In the derivation of the Pearl Index, if the subject did not respond to the question on other contraceptive methods in the subject diary, it will be assumed that another contraceptive method was used. The cycle will be classed as a not at-risk cycle and excluded from the denominator of the Pearl Index. If the subject did not respond to the question on sexual intercourse in the subject diary, it will be assumed that she did not

have sexual intercourse and that cycle will be classed as a not at-risk cycle and excluded from the denominator of the Pearl Index as appropriate.

For compliance, if the number of active (pink) and inactive (white) pills is blank in the diary, then it will be assumed that no pills were taken on that day.

If there is a partial start date for a cycle, then the start date will be imputed as the day after the date of Day 28 of the previous cycle, providing the imputed date is consistent with the non-missing part of the date reported and that the duration of the cycle is consequently consistent with the expected 28 days. For rules around missing or partial start dates for Cycle 1, see Section 5.15.5.

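### The method/user failure label looks at tablet intake over the whole conception cycle, so it can count lapses after conception and miss lapses in the preceding pack

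*SAP*

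**What the plan says.** **Label.** SAP 5.9.4 defines user failure by whether medication was taken "correctly as per Section 9.4.4 of the Protocol during the cycle in which the estimated date of conception occurred", or by use of interacting drugs. The rest follow by default: "Pregnancies not identified as due to user failure will be considered to be method failure pregnancies". Protocol 12.4 allows the user-failure label only where "there is documentation that the subject did not use the test article correctly during the treatment cycle the conception occurred", and counts the missed-pill instructions as part of correct use.

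**Who decides.** SAP 5.9.4: "The pregnancy narratives from the Principal Investigator are used to determine whether a pregnancy is a user or method failure pregnancy". SAP 5.9 has the conception date reviewed together with diary compliance and the narrative, and labels are settled before database lock.

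**Cycle boundaries.** Under SAP 5.1 a cycle lasts until the day before the next recorded start date. SAP 5.7.1 adds: "Any gaps between Day 28 of a cycle and Day 1 of the next cycle will be included as missed pills". Its worked example books the gap days to the earlier cycle.

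**Carry-over recognised elsewhere.** Protocol 9.4.4.3 asks for condom use after a late pack start until active tablets have been taken on 7 consecutive days. Criterion 7 of the compliance-restricted denominator (SAP 5.1.1) accepts a cycle only if this holds: "The length of the previous cycle is not longer than 28 days".

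**The concern.** The method-failure figures are meant to describe pregnancy during correct use. For that, the intake that matters is the intake before conception, whichever pack it came from. The plan takes the calendar unit of the pack instead, and this can go wrong in two ways.

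- **Too wide at the end.** Tablets missed after the EDC in the same cycle satisfy the SAP definition. A true method failure can then leave the numerator. SAP 5.3 closes the on-treatment period at the EDC for women who conceive on treatment, but 5.9.4 does not borrow that limit.
- **Too narrow at the start.** An extended gap just before the pack in which conception occurs belongs to the previous cycle. Unless the back-up instructions were also breached inside the conception cycle, the pregnancy becomes a method failure by default. Yet criterion 7 removes non-pregnant cycles that follow such a gap from the restricted denominator.

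At stake are two secondary efficacy endpoints that rest on few events. The primary Pearl Index counts every on-treatment pregnancy and does not depend on the label.

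**Working it through.** **1. The plan's own figure.** SAP 9.5.1 gives the upper limit as 1300 × ½χ²(0.975; 2(x+1)) / cycles. With a true Pearl Index of 1.0, x is Poisson with mean cycles/1300. At 12,337 cycles the mean is 9.49, the precision target is met for x ≤ 14, and power is 94.0%. At 12,336 cycles it is met only for x ≤ 13, and power is 89.9%. So 12,337 is the first count from which power stays at or above 90%, and the stated figure reproduces.

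**2. Planned exposure and weight of one label.** From SAP 3.1 (1800 women, 45% dropout with 4 cycles on average, 80% of cycles at risk):

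- At-risk cycles: 1800 × (0.55×13 + 0.45×4) × 0.80 = 12,888.
- Expected pregnancies at a Pearl Index of 1.0: 12,888/1300 = 9.9.
- Shift per relabelled pregnancy: 1300/12,888 = 0.10.

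**3. Active tablets that fall after conception but still count** (24 active days, SAP 5.1):

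| Conception day | Active tablets after it | Share of 24 |
|---|---|---|
| 10 | 14 | 58% |
| 14 | 10 | 42% |
| 17 | 7 | 29% |

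**4. Correct-use conceptions open to relabelling.** The documents give no lapse rate, so these are assumptions: a share L of cycles has a qualifying lapse, lapses fall at random over the 24 active days, and the EDC is spread evenly over Days 8-20. The daily lapse probability is p = 1 − (1−L)^(1/24). The share with a lapse after the EDC is the mean over d = 8 to 20 of 1 − (1−p)^(24−d).

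- L = 10%: 0.043
- L = 20%: 0.088

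If all 9.9 expected pregnancies followed correct use, that is 9.9 × 0.043 = 0.4 to 9.9 × 0.088 = 0.9 pregnancies, or 0.04 to 0.09 on the index.

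**5. The preceding pack.** As a yardstick only, take the 7 days before conception, the length of the back-up period in protocol 9.4.4.3. For conception on Day d, 7 − (d−1) of those days lie in the previous pack: 7 for Day 1, 5 for Day 3, 3 for Day 5, 1 for Day 7, and none from Day 8. This error therefore concerns early-pack conceptions. The model in step 4 gives it no size.

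**6. Scale against sampling error.** Suppose 4 method failures in 12,888 cycles. The index is 1300×4/12,888 = 0.40. With ½χ²(0.025; 8) = 1.09 and ½χ²(0.975; 10) = 10.24, the 95% limits are 0.11 and 1.03. One more method failure gives 0.50.

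**7. Check on the obvious repair.** Two of the four method-failure indices in SAP 9.5.2.2 drop non-pregnant cycles with qualifying missed tablets anywhere in the cycle (criteria 5 and 6). If the numerator alone moved to a before-EDC rule, pregnancies with only a later lapse would stay in while comparable non-pregnant cycles were removed. Treating the lapses of step 4 as those of criteria 5-6, the inflation is [mean over d of (1−p)^d] / (1−L): 0.9405/0.90 = 1.05 at L = 10% and 0.8785/0.80 = 1.10 at L = 20%.

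**The case against.** **The label is not mechanical.** Protocol 12.4 states a necessary condition, so a later lapse permits the user-failure label without forcing it. Both documents speak of pregnancies due to user failure, which implies cause, and EDC, diary and narrative are reviewed together before lock. This stands as mitigation, and individual cases may well be labelled sensibly. But SAP 5.9.4 is worded as a definition, and no section gives the reviewers a rule on time order.

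**The preceding pack is partly covered.** A woman who starts late and has not followed the 7-day back-up instruction breaches protocol 9.4.4 inside the conception cycle. That also stands, so it would be wrong to say that late starts are always missed. The diary, however, records condom use and intercourse by cycle (protocol 9.6.1 and 9.6.4.8), so it cannot by itself show what happened in those 7 days.

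**A cycle-level window is robust to dating error.** Conception dates are estimates, some are assigned from the narrative, and SAP 5.9.2 sets the day to not applicable in the 7 days after the last dose. This is fair, and a day-level rule needs a tolerance and a fallback. The mismatch in step 7 is a further valid limit on a simple repair.

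**A reader might also infer that blank diary days create user failures**, because SAP 5.15.1 says that when the pill count "is blank in the diary, then it will be assumed that no pills were taken on that day". The documents do not support this: that rule is confined to compliance derivation, and protocol 12.4 asks for documentation of incorrect use.

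**Conclusion.** The concern holds as a gap in the rule. The stated window has no time order and stops at the pack boundary, so it can give a wrong label in either direction, and at the boundary it is inconsistent with criterion 7. Each wrong label moves the method-failure Pearl Index by about 0.10. At assumed lapse rates of 10-20% per cycle, about 4-9% of conceptions after correct use could be relabelled because of a later lapse, at most 0.04 to 0.09 on the index. That is small beside the sampling error.

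A reader might infer that the rule favours the product. The documents do not show this. Counting later lapses lowers the index, missing earlier ones raises it, and neither frequency is known. In the compliance-restricted indices, whole-cycle exclusion also removes comparable exposure from the denominator. The net direction is unknown, and the primary analysis is untouched.

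**What to change.** In SAP 5.9.4 and protocol 12.4:

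- Base the label on documented incorrect intake dated on or before the EDC, with a stated tolerance for dating error. Fall back to the cycle-level rule where no day of conception can be assigned.
- Look back across the pack boundary, including a late pack start, in line with criterion 7. The sponsor should justify the length of the look-back.
- State that lapses dated only after the EDC do not make a user failure.
- List each pregnancy's lapses by day relative to the EDC.
- For the two compliance-restricted indices, keep numerator and denominator matched, for example by retaining the whole-cycle rule there, and report the other labelling as a sensitivity analysis.

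**Cost:** wording in two documents, one listing and one extra sensitivity table. Conception dates and daily intake are already collected, and every on-treatment pregnancy is already reviewed before lock. The method-failure figure may become slightly less favourable.
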